4.4.2.1 Ordinal Modified Rankin Scale

As a secondary endpoint, mRS at Day 90 will be further explored on the range of the values (0 to 6) where the values of 5 and 6 are grouped. The distribution of full range of mRS scores at Day 90 (imputed) will be summarized by treatment group. Both tabular displays and stacked bar charts will be prepared.

Statistical Analysis Plan: Alteplase—Genentech USMA
15/ML29093 5/17/2017

The comparison will be achieved by fitting a proportional odds model with mRS score at Day 90 as the dependent variable, and treatment group, pre-treatment NIHSS score, age, and last known well time to treatment as the continuous predictors (1, 8). Quadratic terms for the continuous covariates may be added to the model, if the Wald p-value for the quadratic term is <0.1 . No interactions among the covariates will be included in this model. The adjusted odds ratio with its two-sided 95% CI will be shown. Direction of the odds ratio will be chosen to reflect change in the odds of achieving a lower (better) mRS if treated with IV alteplase.

The proportional odds assumption will be tested by the score test, and the p-value will be reported. If the proportional odds assumption does not hold, the resulting odds ratio will not be presented. The alternative analysis planned for this situation will provide the adjusted mean difference between mRS scores with two-sided 95% CI. Methodology for this estimation is similar to the primary outcome, but using the ordinal mRS as the dependent variable.

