4.4.3 Exploratory Efficacy Endpoints

4.4.3.1 Exploratory Analyses for the Primary Endpoint

The primary analysis of the mRS 0-1 outcome will be complemented with exploratory supportive evaluations of treatment group differences.

The following analyses will be conducted to construct risk differences for mRS 0-1. Missing values for day 90 mRS will be imputed in the same manner as for the primary efficacy analysis unless otherwise specified.

Statistical Analysis Plan: Alteplase—Genentech USMA
17/ML29093 5/17/2017

- Unadjusted risk difference.
- Adjusted risk difference, from a linear regression with treatment, age, onset time to treatment, baseline NIHSS, and propensity score as covariates. The propensity score is derived from a logistic regression for treatment group with imbalanced covariates included in the model as covariates. This analysis will be triggered by presence of baseline imbalance. The criteria for baseline imbalance and details of this model are described in [Appendix E](#).

The following analyses will be conducted to construct the odds ratio for mRS 0-1 such that the direction of the odds ratio reflects change in the likelihood of achieving a favorable outcome if treated with IV alteplase:

- Logistic regression, adjusting for pre-treatment NIHSS score, age, and last known well time to treatment as continuous covariates. Quadratic terms for the continuous covariates may be added to the model, if the Wald p-value for the quadratic term is <0.1. No interactions will be included in this model.
- Repeated measures model
mRS outcomes at Day 30 and Day 90 will be modeled jointly by a logistic regression, using the GEE approach to account for the correlation between Day 30 and Day 90 outcomes of the same subject. Detailed description of this model is provided in [Appendix D](#). No imputation will be performed for missing mRS for this particular analysis.

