4.4.4 Subgroup Analyses

For the primary endpoint, consistency of treatment effect of alteplase will be evaluated by various pre-specified baseline covariates. The primary pre-specified variables and their analytic thresholds are defined by:

- Age group (< 65 vs. ≥ 65)
- Pre-treatment NIHSS score group (0-2 vs. 3-5)
- Last known well time to treatment group (0-2 hours vs. > 2 hours)
- Stroke subgroup (RISS vs. non-RISS)

Statistical Analysis Plan: Alteplase—Genentech USMA
19/ML29093 5/17/2017

Adjusted odds ratios by subgroup will be obtained from multivariable logistic regressions with the main effects for treatment, age, last known well time to treatment, and NIHSS, and fit separately for each level of the subgroup.

Interactions of IV alteplase treatment effect with each of the subgroup variables will be explored by adding interactions of the subgroup variables with treatment to the logistic regression. The interactions will be included one at a time; thus, there will be 4 separate models to test each interaction. Results from these models will not be reported, except when the interaction p-values is smaller than 0.1, in which case the p-values will be footnoted in the forest plot.

A forest plot will be constructed to visually illustrate the subgroup analyses. The plot will show the odds ratios described above with two-sided 95% CIs, corresponding to each level of these subgroups. The plot will also show the common odds ratio estimate in different color or line pattern, as a reference. A subgroup analysis will be conducted only if there is at least 10 subjects per outcome (mRS 0-1, mRS >1), and the standard error of the odds ratio estimate is stable with the addition of the covariates.

Analysis of the efficacy endpoints is summarized in [Table 2](#).

Table 2
Summary of Efficacy Analyses

Analysis	Statistical Method	Missing Data Method	Analysis Set(s)
Primary			
mRS 0-1 Day 90	Risk difference via linear regression, CI	LOCF + hot deck	ITT
Secondary			
mRS ordinal Day 90	Proportional odds model Descriptive, frequencies	LOCF + hot deck	ITT
Global outcome measure (Global test)	Logistic regression with a 4-dimensional outcome using GEE	LOCF + hot deck for mRS, non-response for death *	ITT
Exploratory			
mRS 0-1 Day 90	Logistic regression	LOCF + hot deck	ITT
	Logistic regression with Day 30 and Day 90 outcome using GEE	Repeated Measures Model (No imputation)	ITT

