Appendix D

Statistical Methods Requiring Input

Handling of incomplete start and stop dates of adverse events

A missing day in a start date will be imputed with the first day of the month, but not earlier than the randomization date. A missing day in a stop date will be imputed with the last day of the month.

A missing month/year in a start date will be imputed by the month/year of randomization. A missing month in a stop date will be imputed by the month of the last contact. A completely missing stop date will be treated as an ongoing AE and will not be imputed.

Determination of ICH and sICH events

For ICH and sICH events, the following rules will be used to determine their timing relative to 36 hours:

- For ICH determination by scan reading (local or central), take the earliest post-baseline scan with bleeding identified. Use the evaluation time of that scan to compare to 36 hours.
- For ICH determination by AE reporting, take the start date of the corresponding AE. Then find all scans with the same date of local reading, where bleeding is identified. Take the earliest such scan and use the evaluation time of that scan to compare to 36 hours. If no scan is found, use 12:00 am on the AE start date to compare to 36 hours.

When there are multiple scans associated with a PH2 bleed in a subject, the first of these scans will be used to select pre- and post-scan NIHSS scores.

Logistic regression with correlated measures

This model will be used to estimate the odds ratio describing the global favorable outcome, and to estimate the odds ratio of achieving mRS 0-1 at Day 90 in the context of repeated measures.

Statistical Analysis Plan: Alteplase—Genentech USMA
46/ML29093 5/17/2017

The model is specified as follows:

- Let Y_{ik} , be the correlated binary outcomes (1 = favorable outcome, 0 = unfavorable outcome) for patient i , and let $E(Y_{ik}) = \mu_{ik}$ be the marginal means of the outcomes conditional on the patient-specific covariates, including treatment.

For the analysis of the global favorable outcome, $k=1, \dots, 4$ will index the 4 dimensions (mRS, NIHSS, BI, and GOS).

For the analysis of mRS 0-1 $k=1, 2$ will index the repeated evaluations of mRS (Day 30 and Day 90).

- The linear predictor will include an outcome-specific intercept α_k , treatment T_i , and the explanatory variables X_i . The link function transforming the marginal mean outcome μ_{ik} into the linear predictor will be the logit function:

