$$\text{logit}(\mu_{ik}) = \alpha_k + \beta T_i + \gamma_k X_i$$

Importantly, it will be assumed that all outcomes share the same treatment effect β .

- The variance function of Y_{ik} will be determined by the binary distribution variance:

$$\text{Var}(Y_{ik}) = \mu_{ik}(1 - \mu_{ik})$$

- The working correlation matrix structure for the outcomes from the same patient will be assumed to be unstructured:

$$\text{Corr}(Y_{ik}, Y_{im}) = \rho_{km}, k \neq m$$

For the repeated measures model of mRS 0-1, a temporal correlation structure may be chosen instead, which takes into account the distance in time between the repeated measures:

$$\text{Corr}(Y_{i1}, Y_{i2}) = \rho^{|d1-d2|},$$

where $d1$ and $d2$ are study days of Day 30 and Day 90 assessments.

Estimation will be carried out by the generalized estimating equations (GEE).

Adjusted Risk Difference with logistic regression

The logistic regression model defined for the mRS 0-1 outcome provides estimates of the odds of a favorable outcome. These odds can then be converted to probabilities, and thus the risk difference can be obtained as a non-linear contrast

Statistical Analysis Plan: Alteplase—Genentech USMA
47/ML29093 5/17/2017

between the treatment groups. Linearization of this contrast provides an estimate of the standard error, the approximation known as the delta method.

This approach can be implemented with SAS PROC NLMIXED. Here is a sample code:

```
proc nlmixed data=MRS;
  eta=b0+b1*(TRTPN=1)+b2*AGE+b3*OTT+b4*NIHSS;
  p=1/(1+exp(-eta));
  model respn ~ binomial(1,p);
  estimate "tPA vs. Aspirin"
    1/(1+exp(-(b0+b1+b2*&m1+b3*&m2+b4*&m3)) -
    1/(1+exp(-(b0+b2*&m1+b3*&m2+b4*&m3)));
run;
```

where TRTPN=1 selects tPA treatment, and macro variables m1, m2 and m3 resolve to the mean values of AGE, OTT and NIHSS, respectively.

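### The Day 30/Day 90 GEE has a single treatment coefficient, so its odds ratio is the Day 90 odds ratio only if the two visits' effects are equal, and the plan does not check this

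*SAP*

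**What the plan says.** SAP section 4.4.3.1 lists, among the exploratory odds-ratio analyses of the primary endpoint, a model in which "mRS outcomes at Day 30 and Day 90 will be modeled jointly by a logistic regression", using GEE for the within-patient correlation. It adds: "No imputation will be performed for missing mRS for this particular analysis". Table 2 (in section 4.4.4) places this model under the Day 90 mRS 0-1 row. Its method cell mentions both visits, and its missing-data cell begins "Repeated Measures Model (No imputation".

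Appendix D writes one model for two uses. For the global outcome the index k runs over four components. For mRS 0-1, k = 1, 2 "will index the repeated evaluations of mRS (Day 30 and Day 90"). The stated purpose of the second use is "to estimate the odds ratio of achieving mRS 0-1 at Day 90 in the context of repeated measures".

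On the predictor, Appendix D says "The linear predictor will include an outcome-specific intercept" and then gives

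`logit(mu_ik) = alpha_k + beta*T_i + gamma_k*X_i`

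followed by "Importantly, it will be assumed that all outcomes share the same treatment effect".

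**The concern.** The intercept and covariate slopes carry the visit index; the treatment term does not. The model has no parameter belonging to Day 90 alone, yet Appendix D names Day 90 as its target. A common odds ratio is what section 4.4.2.2 sets out to estimate for the four components of the global outcome. For two visits on one scale, it is an extra assumption that the treatment effect does not change between Day 30 and Day 90.

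If the effect does change, the reported odds ratio is pulled towards the Day 30 effect and its confidence interval is centred in the wrong place for Day 90. This matters more in a trial that, after early termination, reports only estimates and intervals (sections 2.3 and 4.4).

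A second consequence is my inference, not a role the SAP assigns. Section 4.4 exempts only this model from mRS imputation, so it is the only mRS 0-1 analysis without LOCF or hot deck. A reader may set it beside the imputed Day 90 logistic odds ratio. A gap between the two could then come from missing-data handling or from the Day 30 effect, and the output could not tell them apart.

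**Working it through.** **1. The SAP's own figures.** The SAP states no value for the repeated-measures odds ratio. The nearest figures are the Table 1 powers in section 2.3, which serve to check how its assumptions are to be read. The inputs are 74% control response among confirmed strokes; 10% mimics with 80% favorable outcome; 1% concomitant tPA; and 290 evaluable patients (145 per arm). The control rate is 0.9 × 0.74 + 0.1 × 0.80 = 0.746. The effects are multiplied by 0.9 (mimics) and 0.99 (tPA). A two-proportion power calculation at one-sided 0.025 then gives 24.6%, 31.1% and 38.4% for 7, 8 and 9 points. Table 1 shows 25%, 31% and 38%, so this reading reproduces it.

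**2. Implied Day 90 odds ratio for the 9-point effect** (ignoring the 1% tPA factor):
- control: 0.746
- alteplase: 0.9 × 0.83 + 0.1 × 0.80 = 0.827
- odds ratio: (0.827/0.173) / (0.746/0.254) = 4.780/2.937 = 1.63

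**3. What the common-beta model estimates.** Without covariates, the large-sample value of beta solves

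`sum over T = 0,1 of D_T' V_T^-1 (p_T - mu_T) = 0`

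Here p_T holds the true Day 30 and Day 90 rates in arm T. `mu_T = expit(alpha_k + beta*T)`, D_T is its derivative, and V_T is the binomial variance combined with the working correlation. If the two true odds ratios are equal, p_T = mu_T is a solution and exp(beta) is that shared value. Otherwise exp(beta) lies between the two in every scenario below.

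Assumptions not in the SAP: Day 30 control rate 65-74.6%; within-patient correlation 0.3-0.7; and the Day 30 odds ratio, which is varied.

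| True Day 30 OR | True Day 90 OR | Model tends to |
|---|---|---|
| 1.00 | 1.63 | 1.13-1.25 |
| 1.21 | 1.63 | 1.31-1.39 |
| 1.40 | 1.63 | 1.46-1.51 |
| 1.63 | 1.63 | 1.63 |
| 1.52 | 1.00 | 1.19-1.28 |

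In the first row, the weight on Day 30 on the log scale is 1 - ln(1.25)/ln(1.63) = 0.54 to 1 - ln(1.13)/ln(1.63) = 0.75. Day 30 thus counts for more than Day 90, the visit of interest.

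**4. Coverage at N = 313.** A separate simulation used a Day 90 odds ratio of 1.72 (74% vs 83%), a Day 30 control rate of 70%, 7.4% of Day 90 values missing at random, and 400 trials per scenario. The 95% interval from the common-beta model covered the true Day 90 odds ratio as follows:
- Day 30 OR 1.0: 71%
- Day 30 OR 1.3: 90%
- equal effects: 95%
- Day 30 OR 2.2: 91%

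A logistic model on Day 90 alone covered 95-96% throughout.

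**5. Contrast within the SAP.** For the ordinal mRS (section 4.4.2.1), "The proportional odds assumption will be tested by the score test", and an alternative analysis is named if it fails. The equal-effects assumption across visits gets neither.

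**The case against.** The assumption is declared openly, for a model whose two uses are both defined just before it. If the effects are equal, exp(beta) is the Day 90 odds ratio, estimated with help from Day 30. A reader might infer that the model can never deliver a Day 90 odds ratio; the document does not support that. This is an unchecked assumption, not an impossibility.

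The labelling is also less misleading than it may look. Section 4.4.3.1 says both visits are modeled jointly, and Table 2's method cell shows it. Only the purpose sentence in Appendix D claims Day 90 outright, with the Table 2 row label in the background.

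A reader might also take this model to be the plan's check on its imputation. It is the only unimputed mRS 0-1 analysis, but the SAP never gives it that role. Nor would a visit-specific effect make it a clean check, because ordinary GEE is in general valid only when data are missing completely at random.

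On size, mild differences do little harm. With a Day 30 odds ratio of 1.40 the shift is from 1.63 to about 1.5. At 145 per arm the standard error of the Day 90 log odds ratio is sqrt(1/(145 × 0.746 × 0.254) + 1/(145 × 0.827 × 0.173)) = 0.29, a 95% interval of roughly 0.92-2.88. The 71% coverage requires no Day 30 effect at all.

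All of this stands, and it limits the weight of the point. It does not remove the mismatch between the stated Day 90 target and a model without a Day 90 treatment term.

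**Conclusion.** The point holds in limited form. As written, the two-visit model yields a pooled odds ratio that matches its stated target only under equal effects at Day 30 and Day 90, with no check and no fallback. Against a true Day 90 value of 1.63, the result ranges from no distortion (equal effects), through 1.46-1.51 (Day 30 odds ratio 1.40), to 1.13-1.25 (no Day 30 effect). The 1.63 follows from the SAP's assumptions. The Day 30 rates, Day 30 effects and correlations are mine, and the calculation omits covariates.

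The severity is minor to moderate. A reader might infer that the main efficacy result is compromised; it is not. The primary risk difference, the crude difference, the Day 90-only logistic odds ratio, the global outcome and the sample size do not depend on this model, and no test or decision rests on it.

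**What to change.** In Appendix D, separate the two uses. For the Day 30/Day 90 model write

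`logit(mu_ik) = alpha_k + beta_k*T_i + gamma_k*X_i`

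that is, add a treatment-by-visit term, and report exp(beta_k) at Day 90 with its two-sided 95% CI. Keep the common beta for the four-component global outcome.

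If the pooled model is preferred, change the purpose sentence in Appendix D and the Table 2 row so that the result is called a common Day 30/Day 90 odds ratio.

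The first option costs one term in the formula and code, and a somewhat wider interval because the Day 30 effect is no longer borrowed. The second costs only wording, but leaves the plan without an unimputed Day 90 odds ratio.

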Appendix E

Documentation of Additional Analyses Performed after Database Lock

Additional analysis for the primary outcome mRS 0-1

Baseline imbalance as measured by standardized difference in additional explanatory variables listed in [Table 6](#) will be explored. The standardized difference can be used to compare the mean of continuous and binary variables between treatment groups. For a continuous covariate, the standardized difference is defined as the difference in the sample means of treatment groups divided by the pooled standard error; see Austin (1) for the mathematical formula. The standardized difference compares the difference in means in units of the pooled standard deviation. Furthermore, it is not influenced by sample size and allows for the comparison of the relative balance of variables measured in different units. Although there is no universally agreed upon criterion as to what threshold of the standardized difference can be used to indicate important imbalance, a standardized difference that is less than 0.1 has been taken to indicate a negligible difference in the mean or prevalence of a covariate between treatment groups (1).

The impact of baseline imbalance if present in at least one candidate variable will be evaluated on the adjusted risk difference for the primary efficacy endpoint through a propensity score approach. Specifically, when there is at least one candidate variable that shows a standardized difference larger than 0.1, propensity scores will be generated using a logistic regression model with the treatment group as the response variable and all variables listed in [Table 6](#) as independent variables. The estimated propensity scores will then be included as an additional covariate in the linear regression model performed for the primary outcome. The adjusted risk difference will be reported from this model. Note that age, baseline NIHSS and onset time to treatment will not be included in the propensity score model, but instead will be explicitly adjusted for in the analysis model.

Missing covariates will be imputed so that all patients have the propensity score defined. Continuous covariates will be imputed with their mean values. Categorical covariates will be collapsed to avoid rare categories. The least frequent categories will be merged together until there are at least 10 subjects per category and the propensity score model has no estimation problems. If there is a substantial number

of missing values in a categorical variable, missing may be considered as a standalone category for the purpose of generating a propensity score.

Table 6
Baseline Characteristics to be Evaluated for Imbalance

Sex	Prior anti-platelet drug use
Race	Prior anti-coagulant drug use
Ethnicity	Baseline glucose
Smoking	Baseline systolic blood pressure
Medical History	Baseline coagulation test: INR
- Hypertension	
- Diabetes Mellitus	
- Atrial Fibrillation	
- Stroke	

Appendix F Data Handling Rules

The data handling rules will be provided as a separate document to be developed in conjunction with any dry runs and finalized before database lock for the interim analysis and separately for the final analysis.

Statistical Analysis Plan: Alteplase—Genentech USMA
51/ML29093 5/17/2017

Abbreviated Clinical Study Report: Alteplase—Genentech, Inc.
812/aCSR ML29093

Appendix G Programming Codes for Statistical Analysis

Calculation of the EQ-5D summary index

```
data LIBNAME.NEWDATANAME ; set LIBNAME.DATANAME ;

/* Generate Dummy Variables for Levels 2 and 3 of Five Dimensions */
m1 =0 ; m2 =0 ;
s1 =0 ; s2 =0 ;
u1 =0 ; u2 =0 ;
p1 =0 ; p2 =0 ;
a1 =0 ; a2 =0 ;

if mobility = 2 then m1 = 1 ;
if mobility = 3 then m2 = 1 ;
if selfcare = 2 then s1 = 1 ;
if selfcare = 3 then s2 = 1 ;
if activity = 2 then u1 = 1 ;
if activity = 3 then u2 = 1 ;
if pain = 2 then p1 = 1 ;
if pain = 3 then p2 = 1 ;
if anxiety = 2 then a1 = 1 ;
if anxiety = 3 then a2 = 1 ;

/* Generate Interaction Terms (I2, I2-squared, I3, I3-squared) */
m0 = 0 ;
s0 = 0 ;
u0 = 0 ;
p0 = 0 ;
a0 = 0 ;

if m1 = 0 and m2 = 0 then m0 = 1 ;
if s1 = 0 and s2 = 0 then s0 = 1 ;
if u1 = 0 and u2 = 0 then u0 = 1 ;
if p1 = 0 and p2 = 0 then p0 = 1 ;
if a1 = 0 and a2 = 0 then a0 = 1 ;

i2 = m1 + s1 + u1 + p1 + a1 ;
i2 = i2 - 1 ;
if i2<0 then i2 = 0 ;
i22 = i2*i2 ;
i3 = m2 + s2 + u2 + p2 + a2 ;
i3 = i3 - 1 ;
if i3<0 then i3 = 0 ;
i32 = i3*i3 ;

/* Generate D1 Term */
i1 = m0 + s0 + u0 + p0 + a0 ;
d1 = 4 - i1 ;
if d1<0 then d1 = 0 ;
```

Statistical Analysis Plan: Alteplase—Genentech USMA
52/ML29093 5/17/2017

```

/* Generate Raw Index Score */
pred = .146016*m1 + .557685*m2 + .1753425*s1 + .4711896*s2 +
      .1397295*u1 + .3742594*u2 + .1728907*p1 + .5371011*p2 +
      .156223*a1 + .4501876*a2 + -.1395949*d1 + .0106868*i22 +
      -.1215579*i3 + -.0147963*i32 ;

EQ_index = 1 - pred ;
if (mobility = .) or (selfcare = .) or (activity = .) or (pain = .) or
  (anxiety = .) then EQ_index = . ;

/* Drop Variables Generated by Program */
drop m1 m2 s1 s2 u1 u2 p1 p2 a1 a2 m0 s0 u0 p0 a0 i1 i2 i22 i3 i32 d1
pred ;

run ;

```

Ordinary Least Squares with Robust Standard Error

```

proc reg data=mrs;
  model mrs = trt age ott nihss / hcc hccmethod=0;
run;

```

Statistical Analysis Plan: Alteplase—Genentech USMA
 53/ML29093 5/17/2017

Data Analysis Plan (DAP) Module 1 Initial Sign-Off

Study title:	A PHASE IIIIB, DOUBLE-BLIND, MULTICENTER STUDY TO EVALUATE THE EFFICACY AND SAFETY OF ALTEPLASE IN PATIENTS WITH MILD STROKE (RAPIDLY IMPROVING SYMPTOMS AND MINOR NEUROLOGIC DEFICITS [PRISMS])		
Protocol #:	ML29093	DAP Version:	1.0

Author:

[Redacted]	[Redacted]	18 May 2017
CRO Study Statistician	Signature	Date

Reviewers:

[Redacted]	[Redacted]	18 May 2017
CRO Peer Review Statistician	Signature	Date

Sponsor Study Statistician	[Redacted]	[Redacted]
	Signature	Date
